## ***8.3. Adverse Events and Serious Adverse Events***

All AEs and SAEs that occur following consent and until the final study visit should be collected and recorded on the AE or SAE eCRF page. Only TEAEs will be summarized ([Section 8.3.1](#)).

All AEs/adverse reactions occurring during the study (i.e., once the subject has signed the informed consent) **must** be documented, regardless of the assumption of causal relationship, on the respective eCRF. All TEAEs/treatment-emergent adverse reactions must be documented from the time the subject receives the study medication until the subject's participation in the study has been completed. If a subject has ongoing AEs/adverse reactions at the time of study completion or discontinuation from the study, the ongoing AEs/adverse reactions **must** be followed up and provided appropriate medical care until the signs and symptoms have remitted or stabilized or until medical assessments have returned to acceptable or pre-study limits.

Documentation of AEs/adverse reactions includes start date and end date, severity, relationship to study medications, action(s) taken, seriousness, and outcome.

### **8.3.1. Adverse Event Definitions**

The following definitions of terms apply to this section:

**Adverse event.** An AE is any untoward medical occurrence associated with the use of a study medication in humans, whether or not it is considered drug related. An AE can therefore be any unfavorable and unintended sign (including abnormal laboratory findings), symptom, or disease temporarily associated with the use of the study medication, whether or not related to the study medication. Study medication includes the investigational drug under evaluation and the comparator product or vehicle placebo that is given or administered during any phase of the study.

Medical conditions/diseases present before starting the investigational treatment are only considered AEs if they worsen after starting the investigational treatment. Abnormal test results

constitute AEs only if they induce clinical signs or symptoms, are considered clinically significant, or require therapy.

The occurrence of AEs should be sought by open-ended questioning of the subject at each visit during the study. At each clinic assessment/visit, study personnel should ask the following question: "Have you had any problems since your last assessment/visit?" AEs also may be detected when they are volunteered by the subject during or between visits or through study assessments.

***Life-threatening adverse event or life-threatening suspected adverse reaction.*** An AE or suspected adverse reaction is considered "life-threatening" if, in the view of either the Investigator or Ocuphire, its occurrence places the subject or subject at immediate risk of death. It does not include an AE or suspected adverse reaction that, had it occurred in a more severe form, might have caused death.

***Serious adverse event or serious suspected adverse reaction.*** An AE or suspected adverse reaction is considered "serious" if, in the view of either the Investigator or Ocuphire, it results in any of the following outcomes:

- Death
- Life-threatening AE
- Inpatient hospitalization or prolongation of existing hospitalization
- Persistent or significant incapacity or substantial disruption of the ability to conduct normal life functions
- Congenital anomaly/birth defect
- Other medically important serious event

Important medical events that may not result in death, be life-threatening, or require hospitalization may be considered serious when, based upon appropriate medical judgment, they may jeopardize the subject and may require medical or surgical intervention to prevent one of the outcomes listed in this definition.

Treatment on an outpatient emergency basis that does not result in hospital admission, or a hospitalization that is elective or is a preplanned treatment for a pre-existing condition that is unrelated to the medication under study and has not worsened since the start of the study, is not considered an SAE.

***Suspected adverse reaction*** means any AE for which there is a reasonable possibility that the drug caused the AE. For the purposes of Investigational New Drug (IND) safety reporting, "reasonable possibility" means there is evidence to suggest a causal relationship between the drug and the AE. Suspected adverse reaction implies a lesser degree of certainty about causality than adverse reaction, which means any AE caused by a drug.

***Unexpected adverse event or unexpected suspected adverse reaction.*** An AE or suspected adverse reaction is considered "unexpected" if it is not listed in the IB or is not listed at the specificity or severity that has been observed. "Unexpected," as used in this definition, also refers to AEs or suspected adverse reactions that are mentioned in the IB as occurring with a class of drugs or as anticipated from the pharmacological properties of the drug but are not specifically mentioned as occurring with the particular drug under investigation.

The study medication relationship for each AE/adverse reaction should be determined by the Investigator using these explanations:

- Not related
- Unlikely related
- Possibly related
- Probably related
- Definitely related
- Unknown

Unless the relationship is considered to be “Not related” or “Unlikely related” and there is any valid reason, even if undetermined, for suspecting a possible cause-and-effect relationship between the study medication and the occurrence of the AE, then the AE should be considered “related.”

If the relationship between the AE/SAE and the investigational product is determined by Ocuphire to be anything other than “Not related” or “Unlikely related,” the event will be considered to be related to the investigational product for the purposes of expedited regulatory reporting.

**Severity** of an AE is defined as a qualitative assessment of the level of discomfort of an AE as is determined by the Investigator or reported to him/her by the subject. The assessment of severity is made irrespective of study medication relationship or seriousness of the event and should be evaluated according to the following scale:

- 1 = Mild: Present, but not distressing, and no disruption of normal daily activity
- 2 = Moderate: Discomfort sufficient to reduce or affect normal daily activity
- 3 = Severe: Incapacitating, with inability to work or perform normal daily activity

A change in severity for a reported AE will require an end date for the previous severity and a new start and end date for the new severity. For example, a change in severity may go from mild to severe or from severe to moderate. In either case the start or end times/dates should be recorded.

The term “severe” is used to describe the intensity of an event/reaction; the event/reaction itself may be of relatively minor medical significance (such as a severe headache). This is not the same as a “serious” AE, which is based on a subject/event outcome or action criteria usually associated with events that pose a threat to the subject’s life or vital functions. “Seriousness” (NOT severity) serves as a guide for defining regulatory reporting obligations.

Should a pregnancy occur, it must be reported and recorded on the pregnancy form and emailed to [REDACTED], as well as in the eCRF. Pregnancy in itself is not regarded as an AE unless there is a suspicion that an investigational product may have interfered with the effectiveness of a contraceptive medication.

The outcome of all pregnancies (spontaneous miscarriage, elective termination, normal birth, or congenital abnormality) must be followed up and documented even if the subject was discontinued from the study.

Action taken in response to an AE is coded as:

- Dose increased: An indication that a medication schedule was modified by addition; either by changing the frequency, strength, or amount.

- Dose not changed: An indication that a medication schedule was maintained.
- Dose reduced: An indication that a medication schedule was modified by subtraction, either by changing the frequency, strength, or amount.
- Dose interrupted: An indication that a medication schedule was modified by temporarily terminating a prescribed regimen of medication.
- Drug withdrawn: An indication that a medication schedule was modified through termination of a prescribed regimen of medication.
- Not applicable: Determination of a value is not relevant in the current context.
- Unknown: Not known, not observed, not recorded, or refused.

Additional other action taken:

- Concomitant medication
- Hospitalization

Outcome of an AE is coded as:

- Fatal: The termination of life as a result of an AE.
- Not recovered/not resolved: One of the possible results of an AE outcome that indicates that the event has not improved or the subject has not recuperated.
- Recovered/resolved: One of the possible results of an AE outcome that indicates that the event has improved or the subject has recuperated.
- Recovered/resolved with sequelae: One of the possible results of an AE outcome where the subject recuperated but retained pathological conditions resulting from the prior disease or injury.
- Recovering/resolving: One of the possible results of an AE outcome that indicates that the event is improving.
- Unknown: Not known, not observed, not recorded, or refused.

In previous clinical studies of Nyxol, the most frequently reported AE was conjunctival hyperemia.

In the present study, any increase of 2 units in conjunctival hyperemia between consecutive timepoints is considered an AE.

Investigators are cautioned to use the appropriate verbatim term on the AE form to describe this observation:

- Redness related to instillation that is transient (i.e., is no longer present 2 hours after instillation) = “conjunctival erythema upon instillation.”
- Redness that is NOT transient (i.e., is present 2 hours after instillation) = “conjunctival hyperemia.”

**Expedited reporting of serious and unexpected adverse events:** All SAEs (related and unrelated) will be recorded following subject signature of the informed consent and until the Safety Follow-Up Call (Visit 3/Day 5). Any SAEs “suspected” to be related to the study medication and discovered by the Investigator at any time **after** the study must be reported.

Any SAE that occurs must be reported to the CRO within 24 hours of its occurrence or within 24 hours of learning of its occurrence. Recurrent episodes, complications, or progression of the initial SAE must be reported to the CRO as follow-up to the original episode within 24 hours of the Investigator receiving the information. Information about all SAEs will be collected and recorded on the SAE eCRF. All pertinent medical records and information collected during the treatment and follow-up of the subject should be maintained at the site with a copy emailed to VEGA1\[contact]. The Investigator must assess the SAE relationship and complete the SAE eCRF. The CRO may request additional information. Follow-up information (e.g., discharge summary) will be retained in the subject's chart and a copy will be emailed to VEGA1\[contact]. In addition, all SAEs should be recorded on the AE eCRF page with the serious question marked "Yes."

It is the Investigator's responsibility to notify the approving IRB of any SAEs on a timely basis as instructed by Ocuphire following Ocuphire's determination of causality. All subjects who experience an SAE should be followed clinically and undergo the appropriate diagnostic evaluations until stabilization or resolution of the event. Ocuphire will report all SAEs to the FDA on the appropriate schedule depending if the event is drug related or not drug related, expected, or unexpected (based on the available information in the IB).

Any death occurring during the study and follow-up period must be reported as an SAE. For any death occurring through the end of the study, regardless of the degree of relationship to study medication, the SAE resulting in the death must be reported to the CRO. A death occurring after completion of the study including the Safety Follow-Up Call, that is not reasonably associated with study medication administration, does not require completion of the SAE form.

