Regarding safety, Nyxol 1% was well tolerated and there were no major ocular or systemic safety issues. An evening dose regimen minimized eye redness during the daytime while benefiting near VA in an elderly population. The incidence of treatment-emergent adverse events (TEAEs) was higher in the Nyxol arm compared with the placebo arm (31.6% versus 5.0%) but all TEAEs were mild in severity, with no serious TEAEs or TEAEs leading to withdrawal or study medication discontinuation. Most TEAEs were considered related to study medication, with the most frequent being conjunctival hyperemia and burning on instillation (each seen in 16% of subjects treated with Nyxol). Although conjunctival redness scores increased in the Nyxol arm at Day 8, Day 15, and Day 16, the scores in the Nyxol arm at any post-baseline timepoint did not demonstrate a statistically significant difference from scores in the placebo arm. Mean systolic and diastolic BPs and HRs were relatively unchanged and remained within normal range throughout the duration of the trial and were similar between arms. Neither biomicroscopic nor ophthalmoscopic examination showed any clinically significant abnormalities at Screening or at Day 15. There was no worsening of distance VA, near VA, or IOP.

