#### **4.4.3. Study Medication Administration**

Treatment 1 study medication will be distributed by the Investigator or designee at Visit 1 after randomization has been assigned. The subject will instill one drop once daily at or near bedtime (approximately 8PM-10PM) OU for 3 to 4 days.

Treatment 2 study medication will be administered by the designated, unmasked, Site Staff member, distinct from the Site Staff member recording measurements/assessments at Visit 2.

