10.1. Adverse Events

AEs will be coded using MedDRA, Version 23.1.

Treatment-emergent adverse events (TEAEs) are defined as any AE that begins or worsens after initiation of the investigational product and through the subject's last study visit (study completion or early termination).

If the onset of an AE is on or after the date of first dose of study medication or is increasing in severity after first dose of study medication, then the AE will be considered treatment emergent.

Only TEAEs will be summarized; all AEs (TEAE, non-TEAE) will be included in a by-subject listing.

The number and percent of subjects with any TEAEs will be summarized by SOC and PT by treatment group and overall. At each level of tabulation (e.g., at the PT level), subjects will be counted only once if they had more than one such event reported during the AE collection period.

Note that in MedDRA, ocular events are coded to the SOC of "Eye Disorders". Thus, using SOC in the summaries will provide a separation of ocular and non-ocular adverse events.

The following summary tables will be presented for TEAE data:

- Overall summary of TEAEs (completed for both the SP and mITT population)
- Summary table of TEAEs by SOC and PT
- Summary table of TEAEs by SOC, PT, and by greatest relationship level to study drug (not related, unlikely related, possibly related, probably related, definitely related, or unknown)
- Summary table of TEAEs by SOC, PT, and maximum severity (mild, moderate, severe)
- Summary table of serious TEAEs by SOC and PT
- Summary table of TEAEs leading to withdrawal from the study by SOC and PT

- Summary table of TEAEs leading to study medication discontinuation by SOC and PT

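### The 2-hour rule that names redness AEs has no scheduled reading after the bedtime drops, and the SAP neither states the preferred term for each name nor adds a combined redness row

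*Protocol*

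**What the plan says.** Protocol 8.3.1 identifies the main known harm: "In previous clinical studies of Nyxol, the most frequently reported AE was conjunctival hyperemia". It sets a graded trigger, under which "any increase of 2 units in conjunctival hyperemia between consecutive timepoints is considered an AE", and then instructs: "Investigators are cautioned to use the appropriate verbatim term on the AE form to describe this observation". Two names follow:

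- *conjunctival erythema upon instillation*, for "Redness related to instillation that is transient (i.e., is no longer present 2 hours after instillation";
- *conjunctival hyperemia*, for "Redness that is NOT transient (i.e., is present 2 hours after instillation".

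On dosing, Protocol 4.4.3 states: "The subject will instill one drop once daily at or near bedtime (approximately 8PM-10PM) OU for 3 to 4 days". Treatment 2 is given by site staff at Visit 2.

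SAP 10.1 codes AEs with MedDRA and states: "The number and percent of subjects with any TEAEs will be summarized by SOC and PT by treatment group and overall". A subject counts once at each level of tabulation. The section lists seven TEAE tables. None is described as pooling the two redness names, and neither document says which preferred term either name will take. The list of planned tables in SAP 12.1 is redacted.

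Graded redness is handled separately. SAP 10.3 gives counts and percentages of the CCLRU grade by arm at baseline and at Visit 2 from 0 minutes to 6 hours, with an ANCOVA.

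**The concern.** The name of the AE depends on the state of the eye 2 hours after a drop. For Nyxol, the drug the protocol links most to redness, those drops are taken at home near bedtime. Protocol 8.3.1 elicits AEs by a general open question about problems since the last contact, with no prompt about redness or how long it lasted. The choice of name for home-drop redness may therefore have little behind it.

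The graded scale does not fill this gap. It is read at visits, and Protocol 2.2 says bedtime dosing was seen to reduce these side effects in the daytime. In the earlier 14-day evening-dosing trial, hyperemia was reported as an AE in 16% of Nyxol subjects while graded scores did not differ significantly from placebo at any post-baseline timepoint. With 19 and 20 subjects that proves little, but it is consistent with AE reports carrying information that morning gradings miss.

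At stake is whether a reader of the AE tables can see how many subjects had redness at all.

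**Working it through.** **1. The plan's own redness rate.** Protocol 2.2 reports "conjunctival hyperemia and burning on instillation (each seen in 16% of subjects treated with Nyxol", from a Nyxol arm of 19. 3/19 = 15.8%, which rounds to 16%; 2/19 = 10.5% and 4/19 = 21.1% do not. So the figure is 3 of 19 subjects.

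**2. Where the 2-hour point falls for Treatment 1.** 8PM + 2 h = 10PM; 10PM + 2 h = midnight. Visit 1 gradings come before the first home drop. The next gradings are on the morning of Visit 2. The documents give no clock time, so assume a start between 7AM and 10AM. The shortest gap is then 10PM to 7AM = 9 h, and the longest 8PM to 10AM = 14 h. No scheduled reading falls at 2 h after a home drop.

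**3. Where it falls for Treatment 2.** Protocol 9.3.6 and SAP 10.3 both schedule a grading at 2 hours on Visit 2. The rule can be applied there.

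**4. From AE form to table.** The sequence is: name written by the investigator, MedDRA coding, count by SOC and preferred term. Two cases follow.

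- *Same preferred term.* Each subject counts once, so that row is already the combined rate. Loss: none.
- *Different preferred terms.* Let the two rows be *a* and *b*. The share of subjects with either lies between max(*a*, *b*) and *a* + *b*, because a subject may appear in both. With *a* = *b* = 7.9%, it could be anything from 7.9% to 15.8%. The SOC row does not resolve this, since it covers all eye disorders.

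**5. Illustration of the second case.** Assumptions: true redness rate 0.158, different preferred terms, no subject under both. The transient shares are arbitrary, as the documents give none. Nyxol subjects: 152 × (4 + 3)/14 = 76, and 76 × 0.158 = 12.0.

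| Share called transient | Transient row | Persistent row | Subjects (transient + persistent) |
|---|---|---|---|
| 0% | 0.0% | 15.8% | 0 + 12 |
| 25% | 4.0% | 11.8% | 3 + 9 |
| 50% | 7.9% | 7.9% | 6 + 6 |
| 75% | 11.8% | 4.0% | 9 + 3 |
| 100% | 15.8% | 0.0% | 12 + 0 |

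A row that counts either name once per subject gives 12 of 76 throughout.

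**The case against.** The strongest reply is that the naming rule follows directly on the 2-unit graded trigger and refers back to that observation. Read that way it names rises seen by site staff, and there the cut can be applied: a 2-hour reading exists after Treatment 2, and a rise seen at Visit 2, 0 minutes has outlasted the evening drop by far more than 2 hours. This reading is fair. But the rule is written in terms of instillation without limiting it to Treatment 2 or to graded rises, and a site that hears about redness after a home drop must still choose a name.

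Several stronger readings are tempting and the documents do not support them.

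- *A reader might infer that the SAP counts the two names separately, so that no AE table gives a redness rate.* The SAP counts preferred terms after coding, and the coding of the two names is not stated. The planned table list is also redacted, so the absence of a pooled row can be asserted only for the tables described in SAP 10.1.
- *A reader might infer that the 2-hour state cannot be known for home drops.* Subjects can notice and report it, and AEs may be volunteered between visits. What is missing is a scheduled observation or a prompt.
- *A reader might infer that the hyperemia rate will look lower than in the earlier trial.* That rate is 3 of 19, with an exact 95% interval of about 3% to 40%. It comes from 14 days of dosing in glaucoma or ocular hypertension, against 3 to 4 days in presbyopia here. Nothing says the earlier figure pooled all redness or was recorded under a different naming rule.

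It is also true that redness is well described at Visit 2 by the graded summaries, that every AE is listed by subject, and that separating brief from lasting redness can be informative. For that reason the separate rows should stay.

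**Conclusion.** The point holds in conditional form. Two parts are firm: no scheduled assessment supports the 2-hour cut after the bedtime drops, and SAP 10.1 neither fixes the coding of the two names nor describes a combined row. The consequence depends on coding. With different preferred terms, the most frequent known Nyxol AE is split over two rows that cannot be summed, and the graded scale does not cover the hours after the evening doses. With one preferred term, the loss is zero.

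The size cannot be estimated from the documents. The 12-subject illustration rests on a rate from 3 of 19 subjects, separate preferred terms, no overlap and arbitrary transient shares. The primary efficacy analysis is unaffected. This is an inexpensive improvement to safety reporting, worth settling before unmasking.

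**What to change.** In SAP 10.1, prespecify a row for conjunctival redness under either verbatim term, each subject counted once. Add it to the TEAE tables overall, by maximum severity and by relationship, alongside the separate preferred-term rows. This row is correct however the names are coded.

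In the AE recording guidance under Protocol 8.3.1, apply the 2-hour naming split only where a 2-hour reading is scheduled, that is, after Treatment 2. Record redness reported after home drops under one term.

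The cost is one derived row from data already collected and a clarifying line for sites. The pooled rate may be higher than either single row, which the table should make plain by showing all three.

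While that text is open, reconcile the graded AE trigger: Protocol 4.1 measures the 2-unit rise between visits, whereas 8.3.1 measures it between timepoints. The choice affects how many redness AEs are recorded at Visit 2.
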